Appendix 2 summarises data collection from study participants.

From service providers:

- **Survey:** VIG practitioners will provide data (through Qualtrics) on the Goal Based Outcomes Scale (3 months) for the VIG group only.
- Interviews: For the process evaluation, VIG therapists (approx. N=5) and service managers (approx. N=3) will be interviewed on their acceptability of the study processes; their perceived effectiveness and implementation issues in relation to VIG offered remotely; barriers and facilitators for engagement with VIG, and contextual service factors that affect VIG delivery.

Participant compensation: There is a small 'thank you' voucher for parents' time to do the research: £10 for screening and then £20 for each data collection (baseline, 3 and 6 months follow up, total £60). An additional £10 data top up could be offered to some participants who need data to fill in the surveys. For parents and clinicians who participate in the process evaluation interviews a '£20' thank you gift voucher will be offered. Compensations are managed by the research team.

Data management and storage: Data will be entered in Qualtrics by participants directly. Participants will be invited via a secure link to complete the questionnaires in Qualtrics; participants can complete Qualtrics questionnaires on their smart phones, PCs, tablets or other electronic devices. Information entered in Qualtrics is then saved directly onto a database. To be able to link the signed informed consent with the baseline and subsequently the two follow up surveys, Qualtrics requires setting up a non-anonymous link between all these elements (these are effectively treated by Qualtrics as four separate surveys). Participants will enter personal data in the consent form and one aspect of their personal data is carried over to the next survey (e.g., email address) so the participant can check it's really them and change their information if they wish. When linked in this way, Qualtrics data are not downloaded all in a single database but separately to protect participants. To further protect participant anonymity, links to surveys are personalised (and emailed to each participant directly), rather than copied on websites or other open invitations. Personal identifying data downloaded from Qualtrics (names, email addresses, telephone numbers) will be kept in a password-protected database separate from the other study data. Study databases will be pseudonymised, i.e., participants will be allocated a code.

The study email address and the Study Co-ordinator's phone number will be provided for parents who need support/have queries or who for whatever reason would prefer to complete the questionnaires in an interview (in this instance the researcher would ask the questions one by one and enter the data directly in the database). Interviews will be transcribed by the Study Co-ordinator or Research Assistants: these will be Master's-level students from UCL who will be on Research Placement with the project (annual commitment) or UCL Master's students doing their dissertation in this study. The team will not use external service providers for transcription. Excel will be used for quantitative data storage. Microsoft Word and NVivo will be the software used for qualitative (including interview files) data storage, assistance with transcription, and qualitative analysis. No visual recordings of interviews will be stored. Transcripts will be anonymised by removal of any identifiable information from the text and a

pseudonym used in place of real names. Audio recordings of interviews will be deleted once the transcript of the interview is completed.

At the end of the data collection period, pseudonymised databases will be shared with UCL for analysis. The data transfer will take place via UCL's Data Safe Haven, a secure data transfer system that encrypts data in transit. The Data Safe Haven has been certified to the ISO27001 information security standard and conforms to NHS Digital's Information Governance Toolkit.

Prior to quantitative analysis, the CI ([name]) and Study Co-ordinator will review the data for any participants who display highly unique 'special characteristics' who may be vulnerable to secondary identification due to their uniqueness. In such cases, the participant will be further protected by analysis criteria being amended so as not to highlight the unique characteristic. For example, if there is only one child from a specific ethnic background, with a specific condition, attending a special needs school then descriptive analysis criteria may be amended so as to reduce exposure in final analysis. Where we publish verbatim quotes from the qualitative analysis, these will be linked to a pseudonym (made up name or code), and pseudonyms will not be linked to participant information in publications.

Intervention fidelity: We will estimate whether VIG is being delivered with fidelity by scoring VIG practitioners using a standardised form. As part of routine clinical practice, VIG practitioners provide support to parents through a process called shared review (see 4.3). Practitioners record themselves when they do a shared review for the purposes of discussing their practice with their VIG supervisor (i.e., recordings of shared reviews are done by VIG practitioners are part of regular clinical practice – not as part of the study). To estimate fidelity, 25 shared reviews will be randomly selected among the 75-125 shared reviews likely generated during the course of the study. [name] (the co-investigator who is an expert on VIG and a VIG supervisor) will code the 25 shared reviews using a standardised form called the Skills Development Scale (VIG-SDS) as she is watching them live/providing supervision in real time. No file transfer is required for this activity: all fidelity coding will take place in real time during supervision meetings. Each VIG practitioner owns and retains their own VIG shared review videos.

The Skills Development Scale (VIG-SDS) includes 11 items rated on a 0-6 scale. VIG-SDS indicates what score is expected from the VIG practitioner dependent on their level of expertise. These scores will be used to estimate fidelity. Scoring the VIG-SDS does not require any information about the parent.

Data Analysis:

Quantitative data will be analysed using descriptive statistics (frequencies, means, standard deviations). Qualitative data will be analysed guided by the MRC framework for process evaluation (Moore et al., 2015): the analysis will combine a bottom-up with a top-down approach to identify key themes emerging in the data across process evaluation domains of context, implementation and mechanisms of impact.

More detail on the proposed analysis to address the primary and secondary feasibility questions is provided here:

Recruitment: The study will note the number of referrals directly from clinicians, the number of people on mailing lists emailed study information, the number of interested parents undergoing screening, number ineligible, reasons for ineligibility, numbers who consent to be randomised, numbers and reasons for refusal to be randomised. The recruitment rate will be estimated from the number of parents found to be eligible for the trial amongst those undergoing formal screening and the number of those screened who are randomised. The criterion to be met is that at least 50% of eligible parents participate, i.e., N=50 from 100 eligible).

Study retention: the percentage of participants who at the 6m follow-up have at least one questionnaire measure completed among all participants who consented to participate in the study. The criterion to be met is that at least 70% of recruited participants are retained at 6m follow up. The percentage of participants who at 6 month follow up provided data on the DBC2 among those recruited (likely primary outcome in the final trial) will be estimated.

VIG completion: the number of recruited participants who received 3 VIG cycles among the recruited intervention group. The criterion to be met here is that at least 80% of participants receive 3 VIG cycles. VIG cycle completion is defined as one meeting to take a video and one meeting to go through the shared review.

Completeness of outcome measures: the number of participants who provide useable data on each study measure, estimated separately at each time point for every measure. The definition of 'useable' data will be pre-specified for each measure in the data analysis plan and it will correspond to having enough items to allow for the calculation of a total or subscale score.

Health economics data analysis: The health economic analysis will take the health and social care perspective. VIG practitioners and other health and social care service use will be costed using unit costs of health and social care (PSSRU; https://www.pssru.ac.uk/project-pages/unit-costs). The total cost of remote delivery of VIG will be reported as well as the extent to which this differs from the costs of providing TAU.

Acceptability of VIG: framework analysis of qualitative data from interviews with parents, VIG therapists and service managers. Acceptability of VIG will be coded with reference to an established framework for assessing intervention acceptability (Sekhon et al., 2017). Thematic analysis will identify key barriers and facilitators for remote VIG separately by stakeholder group.

Feasibility of remote implementation: Thematic analysis of qualitative data from interviews with parents and therapists in terms of stakeholders' perceived effectiveness, likely adaptations and any unintended implementation failures. Quantitative data on VIG fidelity will be estimated by determining the percentage of shared reviews with a VIG-SDS score at the level expected for level of training the practitioner has had. Patient satisfaction with VIG will be measured by summing the 9 ESQ Satisfaction with Care items and comparing them between the two groups (Brown et al., 2014).

Progression to a final trial: A traffic light system will determine readiness for a definitive RCT. It is anticipated that of about 100 families consenting to the study, at least 50 families will be recruited. A hypothesis testing approach will be used to determine the feasibility of recruitment (Lewis et al., 2021): A green signal for recruitment rate is defined as recruiting more than 50% of eligible families, 35-50% amber; and <35% red. With 90% power and 5% one-sided alpha, 97 families will need to be approached. If recruitment is within the amber zone, but above the critical value of 42, then minor changes will be required to improve recruitment, if recruitment is <42 then major changes will be required.

Traffic light signals (Avery et al., 2017) for study retention and VIG completion: A green signal for study retention rate will be to retain >70% of participants at 6m follow-up (60-69% amber, <60% red). A green signal for VIG completion will be >80% completing 3 VIG cycles (65-79% amber; <65% red). These three primary feasibility outcomes will be the basis for determining whether progression to a full trial is possible.

A green signal for measure completeness will be 100% - 80% of useable data for DBC2 scores (likely primary outcome in full trial). Any measure with <70% useable data will be reconsidered.

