7.2 Sampling

7.2.1 Size of sample

As this is a feasibility RCT, no power calculation was used to estimate the target sample size. The recruitment rate of similar studies (Chakkalackal et al., 2017; Coulman et al., 2020) was examined to determine an appropriate recruitment rate for the current study. Subsequently we estimated the adequacy of the proposed recruitment target to address the study's research questions. It is anticipated that of about 100 families consenting to the study, at least 50 participants will be recruited to the study. A hypothesis testing approach will be used to determine the feasibility of recruitment (Lewis et al., 2021). This is one of the three primary research objectives: A green signal for recruitment rate is defined as recruiting 50% of eligible families, 35-50% amber; and <35% red. With 90% power and 5% one-sided alpha, 97 families will need to be approached. If recruitment is within the amber zone, but above the critical value of 42, then minor changes will be required to improve recruitment, if recruitment is <42 then major changes will be required.

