7.3.2 Consent

Written informed consent will be obtained from all study participants prior to *any* data collection, including screening. A Participant Information Sheet will be given to interested participants when they first contact the research team expressing an initial interest about the study (see 7.3) and it will be discussed with them when they meet with the researcher a few days later. Potential participants will have an opportunity to ask questions during that meeting as the researcher will go through the PIS with them. A link to the informed consent form will be emailed to them at the end of that first meeting (and the PIS again). The email address will have been made available by the potential participant when they first contacted the VIG-LD researcher expressing their interest in the study. The consent form was designed following HRA/MHRA guidelines on e-consent.

An 'Independent' survey will be set in Qualtrics just for the consent form: independent here means that it will include just the consent form not the subsequent questionnaires that need to be completed by study participants. The Qualtrics link will be emailed to the potential participant. The participant will have to read and initial the statements and then write their name as signature in this electronic document. The participant will also enter the code for SITE ID that they first encountered in the VIG-LD study brief (given by the site) and then again at the researcher's response to their initial Expression of Interest.

If for whatever reason participants cannot complete the consent in Qualtrics they will be provided with an editable offline version of the consent that they could sign by hand or offline and return by email: the participant could sign by hand and then email the team a photograph of the hand-signed consent or the participant could fill in their name electronically and then save it as a PDF to email it back to the VIG-LD research team.

Once received signed, a copy of the completed consent form as well as the Participant Information Sheet will be emailed to the consenting participant (for their records) and a copy will be retained in the research team (securely stored in the Tavistock server and separate from other data).

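### The recruitment criterion, its 97 families and its cut-off of 42 are tied to three different populations; 97 belongs to eligible parents, and the 90% power holds only if about that many are screened

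*Protocol*

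**What the plan says.** Recruitment is one of three primary feasibility outcomes that decide progression. The protocol describes its base in three ways.

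- **Eligible.** Section 5, Recruitment: "The recruitment rate will be estimated from the number of parents found to be eligible for the trial amongst those undergoing formal screening", together with the number of screened parents who are randomised. The criterion is "at least 50% of eligible parents participate, i.e., N=50 from 100 eligible". The traffic-light limits use the same base: "A green signal for recruitment rate is defined as recruiting more than 50% of eligible families, 35-50% amber; and <35% red".
- **Consenting.** Section 7.2.1, and in nearly the same words section 5, Progression to a final trial: "It is anticipated that of about 100 families consenting to the study, at least 50 participants will be recruited to the study".
- **Approached.** Both sections: "With 90% power and 5% one-sided alpha, 97 families will need to be approached".

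A count then subdivides amber: "If recruitment is within the amber zone, but above the critical value of 42, then minor changes will be required to improve recruitment"; below 42, major changes are required.

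On the order of events, section 7.3.2 states: "Written informed consent will be obtained from all study participants prior to *any* data collection, including screening". The participant flow in Appendix 2 agrees, with signed consent first and the screening meeting after it. Section 2 (Rationale) names the recruitment rate, with engagement, as evidence of the acceptability of remote VIG.

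**The concern.** Approached, consenting and eligible are successive stages of one funnel. They cannot all number about 100 unless almost nobody is lost between them. A test of a proportion has one denominator, and its sample size and cut-off refer to that denominator. If sites took 97 as the number to approach, the eligible group would be smaller than the calculation needs.

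The order of consent and screening adds a question of interpretation. Every parent found eligible has already signed consent. Parents who never reply, lose interest or do not return the form cannot enter the rate, yet section 2 wants the rate to speak to whether families will accept remote VIG. At stake is a go/no-go signal whose colour can depend on which sentence is followed.

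**Working it through.** **Inputs from the protocol.** Null rate 0.35 and target rate 0.50 (red and green limits, over eligible families); one-sided alpha 0.05; power 0.90; 97 families; critical value 42; 50 recruited.

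**Inputs not in the protocol (assumed, shown as ranges).** Consent among families approached, c = 0.20 to 0.70; eligibility among those screened, e = 0.70 to 0.85; share of eligible parents randomised, q = 0.50 to 0.95.

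**1. Reproducing 97 and 42.**

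n = [1.645·√(0.35×0.65) + 1.282·√(0.5×0.5)]² / 0.15² = 90.3

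With continuity correction: n = (90.3/4)·[1 + √(1 + 2/(90.3×0.15))]² = 96.8, so 97.

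Cut-off at 97: 97×0.35 + 1.645·√(97×0.35×0.65) = 41.7 (42.2 with correction), so 42.

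Both figures are right, as the denominator of the tested proportion and its cut-off. The protocol states that proportion over eligible families.

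**2. Exact binomial properties by number of eligible parents.**

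| Eligible | Cut-off | Alpha | Power at 50% |
|---|---|---|---|
| 100 | ≥44 | 0.039 | 0.903 |
| 97 | ≥42 | 0.056 | 0.923 |
| 97 | ≥43 | 0.036 | 0.889 |
| 71 | ≥33 | 0.030 | 0.76 |
| 62 | ≥29 | 0.037 | 0.74 |
| 56 | ≥27 | 0.028 | 0.66 |
| 53 | ≥25 | 0.045 | 0.71 |

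The last four rows are 50/q for q = 0.70, 0.80, 0.90 and 0.95: the eligible parents seen if accrual stops at 50 randomised. Their power is that of the 35% versus 50% test at that size. When the denominator is small only because 50 joined quickly, the observed rate is itself 70% or more and the comparison is not close. The shortfall therefore matters most when eligible parents run short for another reason.

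**3. If 97 is taken literally as approached.** Eligible = 97·c·e. With c = 0.50 and e = 0.85 this is 97×0.425 = 41, below 42 even if all join. To obtain 97 eligible parents, 97/(c·e) must be approached: 164 (c = 0.70, e = 0.85) to 693 (c = 0.20, e = 0.70).

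**4. Count against percentages.** 42/97 = 43%, inside amber. But 42/84 = 50% and 42/120 = 35%, so 42 lies within amber only for 84 to 120 eligible parents. At 56 eligible, 30 randomised is 54%: green by percentage, below 42 by count.

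**5. What the rate leaves out.** With q = 0.90, c = 0.20 and e = 0.70, the rate is 90% over eligible, 0.70×0.90 = 63% over consenting and 0.20×0.70×0.90 = 12.6% over approached. With c = 0.50 and e = 0.85 the three are 90%, 76.5% and 38%.

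**6. Chance of green (above 50%) on the eligible base.** 0.46 if q = 0.50 (100 eligible); 0.97 if q = 0.60 (83 eligible); above 0.999 if q ≥ 0.70 (71 or fewer). These treat the eligible number as fixed.

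**The case against.** The best defence is that the plan is sound and one word is loose. The definition, criterion and limits in section 5 all use eligible families and foresee 100 of them, and at that number the calculation delivers what it claims. This stands, and it rules out one stronger inference: that the 90% power simply does not apply. It applies if about 97 to 100 eligible parents accrue. Nor can one say that 42 is unreachable, because no sentence says approaches stop at 97. Nor is the 97 ever stated over consenting families; that word belongs to the separate sentence about 100 families.

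A reader might also infer that green is nearly automatic, since everyone in the denominator has consented. The protocol does not support that either. It counts refusals to be randomised after screening, gives no rate for them, and itself expects 50 of 100. Parents may also be lost during a screening interview that can need a second appointment, or at the baseline assessments that precede randomisation.

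Lastly, widespread refusal would be visible. Sites report monthly how many families received the study brief, reasons for not consenting are invited, VIG completion is a separate criterion, acceptability is explored at interview, and the steering committee gives an independent view of the progression outcomes. This is true, but none of it enters the recruitment signal, and it does not reconcile the three bases.

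**Conclusion.** The point holds as a contradiction in a primary progression criterion. The figures 97 and 42 are correctly calculated but, in the sample-size sentence, attached to the wrong population. Read over eligible parents they give exact power of 0.89 to 0.92; with 53 to 71 eligible, power is 0.66 to 0.76. A fixed count of 42 agrees with the amber band only between 84 and 120 eligible.

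The eligible-based rate measures conversion from consented and eligible to randomised. It cannot by itself show acceptability among families approached, and it may be green when most of them declined. How likely that is depends on post-consent losses that the protocol does not give: the chance of green runs from 0.46 to above 0.999 as the share randomised goes from 50% to 70% or more. The power figures and the reproduction of 97 and 42 need only the protocol's limits and a given eligible number; the funnel figures rest on the assumed ranges.

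**What to change.** Use one denominator for the rate, the traffic-light limits, the 97 and the 42, in both parts of section 5 (Recruitment; Progression to a final trial) and in section 7.2.1. If eligible parents are kept:

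1. Say that 97 families must be screened and found eligible, and restate the expected 50 of about 100 on that same base.
2. State that the 90% power applies only if about 97 eligible parents accrue.
3. Replace the fixed 42 by a proportion (42/97 = 43%) or recompute it for the eligible number observed. Exact one-sided 5% cut-offs are, for example, 44 at 100, 43 at 97 and 33 at 71.
4. Report randomised/approached, from the monthly site counts, and randomised/expressed interest, from the research team's recruitment database, beside the signal. Do not read the eligible-based rate alone as evidence of acceptability.

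Moving the signal to expressions of interest minus those screened ineligible would not solve the problem. In an assumed funnel of 400 given the brief, 120 interested, 100 screened, 55 eligible and 50 randomised, it gives 50/(120−45) = 67%, still green although 280 families never responded.

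The cost is protocol wording; the counts are already collected. The reported picture may be less favourable.

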Study Design: A feasibility randomised controlled trial of 50 parents allocated on a 1:1 basis into intervention or treatment as usual (TAU), with an embedded process evaluation. We will collect service use data for cost comparison in a parallel feasibility economic evaluation. This will be conducted by a series of questionnaires and interviews.

Randomisation

Randomization will take place after participants have consented to the study and have had their eligibility confirmed by the screening process. Participants will be randomized on a 1:1 basis to the two study arms (VIG+ treatment as usual vs treatment as usual). The randomisation will be performed by the study statistician at the Cardiff Centre for Trials research.

Data collection methods:

From study participants:

- Interviews: Parents will be interviewed to determine eligibility to be included in the study; in addition to a few questions matching the inclusion/exclusion criteria, parents will be administered the Vineland-3 (Sparrow et al., 2016) to determine their child's overall adaptive skills score. Parents who enter the study will be interviewed to measure their levels of service use (CA-SUS; Byford et al., 1999) at baseline (before randomisation) and 6 months after randomisation.

 For the process evaluation, approximately 10 parents (five from each group) and approximately eight clinical staff (including VIG clinicians and Service Managers) will be interviewed at the 6-month follow up (semi-structured interviews) to investigate their experience of the study (intervention and evaluation acceptability); perceived effectiveness of VIG and implementation issues (VIG group only); barriers and facilitators for engagement with VIG (VIG group only), and contextual service factors that affect VIG delivery (VIG group only). Interviews will take place over the telephone or an online video platform (Teams or Zoom). Interviews will last between 30 minutes to one hour.

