11.2 Appendix 2 - Schedule of Procedures

Participant flow to the study

Sites > Study Brief for participants (mailout or in clinical consultation)

Potential participants contact Researcher (email or phone)

Telephone appointment with researcher to go through PIS and give consent form

Consent signed > Meeting with researcher for screening

Eligible and Consenting Parti	cipants			
Procedures	Screening	Baseline	3 months	6 months
Vineland Adaptive Behavior Scale 3 Domain-level version	X (interview)			X (socialisation and communicatio n items only – survey)
Demographics		х		
Developmental Behaviour Checklist 2 (DBC2)		х		х
Child-Parent Relationship Scale- Short form (CPRS)		х	х	х
Patient Health Questionnaire- 4 item (PHQ-4)		х	х	х
Alabama Parenting Questionnaire – positive parenting and inconsistent discipline		х	х	х
Parenting Sense of Competence (PSEC) – self efficacy		х	х	х
Goal Based Outcomes- Intervention group only			х	
Support from Specialist mental health team and satisfaction with service			х	
Child and Adolescent Service Use Scale (CA-SUS) - Interview		х		х
Parent Interview (Process evaluation)				х
Clinical Staff Interview (process evaluation)				х

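### The 6-month retention rate, a primary progression outcome, has two conflicting denominators: everyone who consented, and those recruited

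*Protocol*

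**What the plan says.** Section 4.1 lists retention at 6 months as one of three primary feasibility questions. Section 5 (Progression to a final trial) makes those three outcomes the basis for deciding on a full trial. The denominator for retention appears in four places:

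- **Definition** (section 5, Study retention): participants who at 6 months "have at least one questionnaire measure completed among all participants who consented to participate in the study".
- **Criterion** (the next sentence): "The criterion to be met is that at least 70% of recruited participants are retained at 6m follow up".
- **Companion figure for the likely primary outcome** (same paragraph): those who "provided data on the DBC2 among those recruited (likely primary outcome in the final trial) will be estimated".
- **Traffic-light rule** (section 5, Progression to a final trial): "A green signal for study retention rate will be to retain >70% of participants at 6m follow-up (60-69% amber, <60% red".

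On the order of events, section 7.3.2 states: "Written informed consent will be obtained from all study participants prior to" any data collection, and it names screening as included. Appendix 2 gives the sequence "Consent signed > Meeting with researcher for screening". Section 5 (Randomisation) adds: "Randomization will take place after participants have consented to the study and have had their eligibility confirmed by the screening process". On numbers, section 5 (Progression) says "It is anticipated that of about 100 families consenting to the study, at least 50 families will be recruited", and section 7.2.1 gives the same expectation. The planned randomised sample is 50.

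**The concern.** Consent comes before screening, so those who consented include parents later found ineligible and parents who decline randomisation. Follow-up dates are set at 3 and 6 months after randomisation (section 5, Questionnaires). A parent who is never randomised therefore has no 6-month date and cannot enter the numerator, yet the definition keeps that parent in the denominator.

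The sentence that follows uses a different group for the same outcome. The same follow-up data can then be red under one sentence and meet the criterion under the next. If the choice is made after the data are seen, that choice decides the signal. The consent-based rate also counts loss before randomisation twice, once in the recruitment rate and again in retention.

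**Working it through.** **The plan's own figure.** The protocol gives no calculation for retention. Its only formal calculation is for recruitment (35% v. 50%, one-sided 5%, 90% power), and it reproduces:

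- Uncorrected: n = [(1.645·√(0.35·0.65) + 1.282·√(0.5·0.5)) / 0.15]² = 90.3.
- With continuity correction: (90.3/4)·[1 + √(1 + 2/(90.3·0.15))]² = 96.84, so 97, as stated.
- Critical value: 97·0.35 + 1.645·√(97·0.35·0.65) + 0.5 = 42.2, so 42, as stated.

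That arithmetic is sound and says nothing about the retention denominator.

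**Inputs for retention.** About 100 consenting and at least 50 recruited (section 5, Progression; section 7.2.1); 50 randomised (section 5, Study Design); red below 60%, amber 60–69%, green above 70%. I take recruited to mean randomised.

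**Formulas.** With R randomised, C consented and r the proportion of the randomised who are followed up:

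- rate on the definition = R·r / C
- rate on the criterion = R·r / R = r

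**At the planned figures (R = 50, C = 100):**

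| Followed up | On the definition | On the criterion |
|---|---|---|
| 50 | 50/100 = 50% (red) | 50/50 = 100% |
| 45 | 45/100 = 45% (red) | 45/50 = 90% |
| 40 | 40/100 = 40% (red) | 40/50 = 80% |
| 35 | 35/100 = 35% (red) | 35/50 = 70% |
| 30 | 30/100 = 30% (red) | 30/50 = 60% |

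The 35/50 row meets the criterion of at least 70%. It is not strictly green, because green is above 70%; 36/50 = 72% is green, against 36/100 = 36%, red.

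**Sensitivity to the number consenting (R = 50).** The values 110 and 125 are illustrative.

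| Consented | No loss | 70% of randomised retained |
|---|---|---|
| 97 | 51.5% | 36.1% |
| 100 | 50.0% | 35.0% |
| 110 | 45.5% | 31.8% |
| 125 | 40.0% | 28.0% |

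**When the literal definition could leave red.** With 50 randomised and no loss, amber needs C ≤ 50/0.60 = 83.3, so 83 or fewer. Green needs C < 50/0.70 = 71.4, so 71 or fewer. In general, amber needs R/C of at least 60% with no loss, or 0.60/0.80 = 75% if 80% of the randomised are retained. The planned ratio is 50%.

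**The case against.** A reader might infer that retention cannot leave the red zone, or that the go/no-go rule is bound to give the wrong answer. The protocol does not support that, for two reasons.

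- The sentence carrying the 70% threshold is set over recruited participants, as is the DBC2 figure, and VIG completion is set over the recruited intervention group. No threshold is attached to everyone who consented. On the recruited denominator all three zones can be reached.
- The 50% ceiling is a planning ratio. The text says about 100 and at least 50. The 100 is also described as eligible parents in the recruitment paragraph, and 97 families are to be approached. If the 100 are eligible, those consenting before screening number at least 100 and the ceiling is 50% or lower. If only 97 are approached, consenters could be fewer and the ceiling higher.

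A narrower reading of consent is also open. The recruitment paragraph counts parents who consent to be randomised after counting the ineligible, and section 7.3.2 and Appendix 2 both speak of participants who are eligible and consenting. On that reading the two denominators coincide. It is the weaker reading. Section 7.3.2 describes one consent form for trial entry, signed before screening, and the only separate form is for the process-evaluation interviews. The progression paragraph also sets families who consent apart from families who are recruited within one sentence.

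It may be added that the steering committee gives an independent view on the progression outcomes, and that the team probably intends recruited participants. Both are likely true, but neither tells the committee which sentence governs.

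**Conclusion.** The concern holds as an inconsistency: one primary progression outcome has two stated denominators, and the traffic-light rule does not choose between them. At the planned figures the definition caps retention at 50%, while the criterion can reach 100%; the definition gives exactly half the criterion's rate at any level of follow-up. This size rests on 50 randomised out of about 100 consenting, on recruited meaning randomised, and on consent meaning the form signed before screening. If a larger share of consenters were randomised the gap would narrow, but the two statements would still conflict. The matter is not one left to an analysis plan, because the protocol fixes the denominator and then contradicts it. Sample size, data collection and conduct are unaffected.

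**What to change.** Make four changes to section 5:

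1. In the retention definition, replace the reference to everyone who consented with *all randomised participants*.
2. In the 70% criterion, replace *recruited participants* with *randomised participants*.
3. In the traffic-light rule for retention, which now says only *participants*, write *randomised participants*.
4. Report the loss between consent and randomisation under recruitment. The recruitment paragraph already plans to count the ineligible and those who refuse randomisation.

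The cost is a short wording amendment with no new data. It should be made before 6-month retention is assessed, so that the denominator is not chosen with the result in view.
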